#### **6.1.2 Treated Population (TP)**

The “treated” population is defined as all subjects who have received any amount of study drug treatment.

Safety assessment are performed using the treated population.

The treated population will also be analyzed for the PK parameters, as supportive evidence to the PK profiles.

### **6.1.3 The “Intent-To-Treat” Population (ITT)**

The ITT population is defined as all subjects who have been randomized and are treated or untreated with the study treatment.

### **6.1.4 Analysis with Randomization Code Deviation**

Analysis of ITT and TP are not BE determination analyses. In cases where a subject’s actual treatment has deviated from the randomized treatment assignment (which has been confirmed by site investigator(s) and Amphastar quality assurance), analysis of TP will follow the actual treatment received. Conversely, analysis of the ITT will follow the original randomization assignment.

However, the analysis for PPP, which is the determination analysis for BE, will exclude the subject with a deviation from the randomization code as specified in Section 5.1.1.

## **6.2 MISSING DATA HANDLING**

### **6.2.1 Missing Data Handling for Evaluable Subjects**

For an evaluable subject that was defined in Section 6.1.1, only a small portion of PK measurements, if any, are allowed to be missed, and the interpolation method will be used for imputation.

If the PK data at t=12 hrs is missed, the exploration method is allowed.

### **6.2.2 Missing Data Handling for Non-Evaluable Subjects**

Non-Evaluable Subjects will be excluded from primary and secondary analysis.

## 6.3 DATA SETS

The data sets are defined based on the following two factors: (i) laboratory analysis and (ii) severe protocol deviation (SPD) assessment by the Management Review Board (MRB), constituted by the Quality Assurance (QA) department, Clinical Operations, the Clinical Science Group, and Regulatory Affairs.

### 6.3.1 The PK Datasets

The PK data based on PK sample analysis will have two sets of results:

- Final Reported Data (FRD): the results finally reported by the laboratory for PK analysis, which will include results from re-assayed samples due to various reasons, such as (i) out of calibration range, (ii) correction of laboratory error, etc.
- Initially Tested Data (ITD): the results reported by the laboratory for PK analysis, which will include only initial test results data, without any re-assay. It is acknowledged that ITD may have some incorrect data.

### 6.3.2 Severe Protocol Deviation Assessed by Management Review Board

The Management Review Board (MRB) may determine that some data should be excluded from PPP analysis due to severe protocol deviation (SPD). SPD include, but are not limited to,

- Full dose of study drug not administered (ICH category III);
- Use of prohibited drugs (ICH category IV);
- Violating drug, alcohol, or caffeine restriction;
- Sample handling (extreme deviations of sample isolation time, centrifuge time, sampling record etc.); and
- Severe out of the sampling window time (see **Section 5.6.3**).

The data for excluded samples due to SPD will be considered missing data (see **Section 5.2**).

Thus, two datasets will exist for

- SPD-excluded (SPD-E) dataset: identified SPD data are excluded and are considered as missing data;
- SPD-included (SPD-I) dataset: identified all SPD data are still used in the data analysis.

### 6.3.3 Datasets used for Statistical Analysis

Combining the above two factors, in total there are four (4) datasets for PK and PD evaluation as summarized in **Table 5**, and **Table 6**, respectively below:

**Table 5. Datasets for I004-B: PK Evaluation**

Factors to Determine Datasets			Laboratory PK Data Analysis	
			Initially-Tested Data (ITD)	Final Reported Data (FRD)
Assessment for Severe Protocol Deviation (SPD)	No SPD Observed	-	ITD	FRD
	SPD Observed	SPD-excluded (SPD-E)	ITD + SPD-E	FRD + SPD-E
		SPD-included (SPD-I)	ITD + SPD-I	FRD + SPD-I

The PK BE statistical analysis will be conducted for all four (4) datasets (**Table 5**). Among the datasets, the final reported data for SPD-excluded (FRD + SPD-E) dataset is the most reasonable one and should be considered as the formal results for PK evaluation.

**Table 6 Datasets for I004-B: PD Evaluation**

Factors to Determine Datasets			Final Reported Data for PD (FRD)
Assessment for Severe Protocol Deviation (SPD)	No SPD Observed	-	FRD
	SPD observed	SPD-excluded (SPD-E)	SPD-E=FRD
		SPD-included (SPD-I)	SPD-I

The PD BE statistical analysis will be performed for all two (2) datasets (**Table 6**). Among the datasets, the final reported data for the SPD-excluded (FRD + SPD-E) dataset is the most reasonable one and should be considered as the formal results for the PD evaluation.

## 6.4 STATISTICAL ANALYSIS

### 6.4.1 Demographic Data

Demographic data and baseline characteristics are reported for each subject. For all subjects as one group, continuous variables will be summarized with n, mean, and standard deviation, while frequency counts and percentages of subjects within each category will be provided for categorical data.

### 6.4.2 Endpoints Evaluation

#### 6.4.2.1 Primary Analysis

The objective of this study is to assess and compare the PK/PD profile of I004 and Novolog.

The geometric mean ratio and confidence intervals of the primary analyses should meet FDA bioequivalence requirements: the 90% confidence interval is within 80.00 – 125.00%.

The two (2) null hypotheses for the standard two one-sided tests procedure are :

$$H_{01}: \mu_T - \mu_R \leq \theta_1 \quad (31)$$

$$H_{02}: \mu_T - \mu_R \geq \theta_2 \quad (32)$$

and the alternative hypothesis is:

$$H_a: \theta_1 < \mu_T - \mu_R < \theta_2 \quad (33)$$

where, for PK dataset,  $\mu_T$  and  $\mu_R$  are the natural logarithms of geometric means of  $C_{max}$  and  $AUC_{IA(0-12h)}$  for serum IA concentration of Treatment T and Treatment R, respectively; for PD dataset,  $\mu_T$  and  $\mu_R$  are the natural logarithms of geometric means of  $GIR_{max}$  and  $AUC_{GIR(0-12h)}$  for smoothed GIR curve of Treatment T and Treatment R, respectively.

The parameters  $\theta_1$  and  $\theta_2$  are equal to  $-0.223$  (i.e.,  $\ln 0.8$ ) and  $0.223$  (i.e.,  $\ln 1.25$ ), respectively.

PK/PD endpoints will be analyzed using ANOVA methods with the effects of Treatment groups, Period, Sequence and Patient-within-Sequence. The following model is used:

$$Y_{ijkh} = \mu + T_j + Q_k + P_h + S_{i,k} + e_{ijkh} \quad (34)$$

where  $\mu$  is the overall mean of the natural logarithms of  $C_{max}$ ,  $AUC_{0-12hr}$  and  $GIR_{max}$ ,  $AUC_{GIR(0-12hr)}$  denotes the effect of the  $j$ th treatment,  $Q_k$  denotes the effects of  $k$ th sequence,  $P_h$  denotes the effect of the  $h$ th period,  $S_{i,k}$  denotes the effect of  $i$ th subject nested within  $k$ th sequence, and  $e_{ijkh}$  is independent random errors in observing  $Y_{ijkh}$ . For 2x2 crossover design as this study, random errors  $e_{ijkh}$  follow the distribution  $N(0, \sigma)$ , where the population standard deviation  $\sigma$  can be approximated as:

$$\sigma \approx s = \sqrt{MSE} = \sqrt{\frac{SSE}{n_{AB} + n_{BA} - 2}}. \quad (35)$$

The mean square error (MSE) and the sum of square error (SSE) will be obtained directly from the SAS output.

The 90% confidence intervals (CI) will be computed as follows:

$$90\%CI = \Delta \pm t_{1-\alpha/2, df} \times \sigma \quad (36)$$

where  $\alpha=10\%$ , and  $\Delta$  is the difference of least square means of the logarithms of PK/PD endpoints for treatments T and R.

After being transformed back from the logarithm form, the result per Eq. (27) becomes the 90% confidence intervals of the geometric mean of the ratio of PK/PD parameters (T/R).

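### SAP Eq. (36) builds the 90% CI from the residual SD instead of the standard error of the T-R difference, so the bioequivalence interval is too wide (5.48 times on the log scale at 30+30) and does not narrow as n grows

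*SAP*

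**What the plan says.** SAP section 6.4.2.1 sets a conventional target. The hypotheses open with "The two (2) null hypotheses for the standard two one-sided tests procedure are", with limits ln 0.8 and ln 1.25, and the acceptance rule is that "the 90% confidence interval is within 80.00 – 125.00" percent. The model (Eq. 34) is the usual 2x2 crossover ANOVA on log-transformed endpoints, with treatment, sequence, period and subject-within-sequence effects.

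The interval is then built in two steps:

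- Eq. (35) concerns the random errors of that model, "where the population standard deviation" σ being approximated by sqrt(MSE) = sqrt[SSE/(n_AB + n_BA − 2)]. The text adds: "The mean square error (MSE) and the sum of square error (SSE) will be obtained directly from the SAS output".
- Eq. (36) follows the words "The 90% confidence intervals (CI) will be computed as follows" and reads Δ ± t(1−α/2, df) × σ. The explanation after it covers only α (10%) and Δ (the least-squares-mean difference). The symbol σ is not redefined, and df is not stated.

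The next sentence says that the back-transformed result of Eq. (27) "becomes the 90% confidence intervals of the geometric mean of the ratio of PK/PD parameters (T/R"). Eq. (27) is the formula in SAP section 5.2.2 for the time to 50% of maximal GIR before the peak. Section 6.4.2.2 carries a similar analysis over to the secondary endpoints.

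**The concern.** A 90% confidence interval for a treatment difference needs the standard error of that difference. Eq. (36) uses the SD of a single residual error instead. The sequence sizes enter only as the error degrees of freedom in Eq. (35), so nothing in the width reflects how many subjects were averaged.

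This interval is the only stated bioequivalence criterion for the four primary endpoints (Cmax and AUC(0-12h) of insulin aspart, and GIRmax and AUC_GIR(0-12h)). If the formula is followed, an equivalent product can fail because of the formula alone. If the analysis program uses the standard interval instead, the pivotal result departs from its SAP on the deciding calculation, and in the sponsor's favour. Such a departure is hard to defend once data have been seen.

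**Working it through.** **Inputs**

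- n_AB = n_BA = 30: Protocol section 6.6, Table 6-2.
- df = 30 + 30 − 2 = 58, the divisor in Eq. (35); t(0.95, 58) = 1.6716.
- Margin: 80.00–125.00%, SAP section 6.4.2.1.
- Within-subject CV and true geometric mean ratio (GMR): not in the available text. Assumed here: CV 10–30%, GMR 1.00 and 0.95, with σ = sqrt[ln(1 + CV²)].

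**The plan's own figures.** ln 0.8 = −0.2231 and ln 1.25 = 0.2231, which agree with the stated ±0.223. The sample size of 60 (Protocol section 10.3) cannot be reproduced because no CV, GMR or power is available. Those inputs may have been redacted, so this is not counted as an error.

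**Standard error under Eq. (34).** Each subject's T-R difference has variance 2σ² once the period effect is removed. Δ is the average of the two sequence means of these differences, so

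Var(Δ) = ¼ × 2σ² × (1/n_AB + 1/n_BA) = σ² × 0.5 × (1/n_AB + 1/n_BA).

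At 30+30 the factor is sqrt[0.5 × (1/30 + 1/30)] = sqrt(1/30) = 0.1826. As a check, the Eq. (34) model was fitted to one simulated 30+30 data set. It gave residual df 58, root MSE 0.2220 and standard error 0.0405, a ratio of 5.477.

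**Half-widths on the log scale, 30+30**

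- Eq. (36): 1.6716 × σ.
- Correct: 1.6716 × 0.1826 × σ = 0.305 × σ.
- Ratio: 1/0.1826 = 5.48. It is 5.00 at 25+25, 5.20 at 27+27 and 5.74 at 33+33.

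**Example, CV 20%, observed GMR 1.00.** σ = sqrt(ln 1.04) = 0.198. Eq. (36) gives exp(±0.331) = 71.8–139.2%. The correct interval is exp(±0.0604) = 94.1–106.2%.

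**Largest CV that can pass**

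- Eq. (36), observed GMR 1.00: σ must be below 0.2231/1.6716 = 0.1335, so CV below 13.4%.
- Eq. (36), observed GMR 0.95: CV below 10.3%.
- Correct standard error: 84% and 61% respectively.

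Sample size hardly moves the Eq. (36) limit, which is 13.4% at both 25+25 and 33+33. With unlimited n, t falls only to 1.645, so the limit is σ = 0.2231/1.645 = 0.1356, or CV 13.6%. The correct limit rises from 75% at 25+25 to 90% at 33+33.

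**Single-endpoint pass probability, 30+30 (400,000 simulated trials per scenario)**

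| Assumed CV | GMR 1.00, Eq. (36) | GMR 1.00, correct | GMR 0.95, Eq. (36) | GMR 0.95, correct |
|---|---|---|---|---|
| 10% | 0.98 | 1.00 | 0.60 | 1.00 |
| 12% | 0.63 | 1.00 | 0.17 | 1.00 |
| 15% | 0.04 | 1.00 | 0.01 | 1.00 |
| 20% | 0.00 | 1.00 | 0.00 | 1.00 |
| 30% | 0.00 | 0.99 | 0.00 | 0.94 |

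**Direction.** The factor is below 1, so the Eq. (36) interval always contains the correct one. Any result that passes under Eq. (36) also passes with the correct standard error, so the false-positive rate cannot rise.

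**The case against.** The strongest reply is that σ in Eq. (36) is a notation slip for the standard error of Δ. The section names the standard two one-sided tests, a standard crossover ANOVA and a least-squares-mean difference. The protocol synopsis (part VI, Statistical Analysis) asks for 90% CIs of the ratio of geometric means, which Eq. (36) read literally does not give. SAP section 6.6.3 says that the analysis programs are validated. A program that takes the T-R contrast from SAS would report the right interval. This is plausible, and the documents do not show which route the program takes. It does not change what the SAP prespecifies: σ is defined once, one equation earlier, as the residual SD, and no section supplies the missing term.

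A second caution is text extraction. In the definitions under Eq. (34), the symbol for the treatment effect is missing before its description. A term lost from Eq. (36) is therefore possible, and the source PDF should be checked. However, Eq. (36) reads as complete, and the explanation after it mentions no standard error.

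Three stronger readings are tempting, and the documents do not support them:

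- **The study cannot pass, or an equivalent product must fail.** The documents give no CV, and an endpoint with a CV of 10% and a true GMR of 1.00 would still pass 98% of the time.
- **Every interval is 5.5 times too wide.** That figure belongs to 30+30 on the log scale. The PK and PD per-protocol populations (SAP section 6.1.1) have different evaluability rules, so n may differ between endpoints.
- **Eq. (36) is an interval for an individual.** A single subject's T-R difference has SD sqrt(2) × σ, so it is not that either. What can be said is that its width does not shrink with n.

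The Eq. (27) reference is a numbering error and adds no weight.

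**Conclusion.** The point stands. Eq. (36) is wrong as written for the sole 80.00–125.00% decision rule. The size of the width error (5.48 at 30+30) needs no assumption beyond the Eq. (34) model and the number of evaluable subjects per sequence. The consequence depends on the assumed CV: a false failure is very likely from about 15% upward, whatever the sample size, while an endpoint with a CV below about 13.4% and an observed GMR of 1.00 can still pass. The pass probabilities are for one endpoint; requiring several to pass together cannot raise them. The risk is a false failure of bioequivalence, not a false claim of it.

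**What to change.** Replace Eq. (36) with

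90% CI = Δ ± t(0.95, n_AB + n_BA − 2) × sqrt[MSE × 0.5 × (1/n_AB + 1/n_BA)],

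with n_AB and n_BA the evaluable subjects per sequence for the endpoint concerned. Alternatively, specify the 90% CI of the T-R least-squares-mean contrast from the SAS ANOVA. Confirm that the analysis program does the same. As an editorial correction, change the reference to Eq. (27) in the back-transformation sentence to Eq. (36).

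The cost is one line of SAP text plus the cross-reference. No data collection or subject burden is involved. The correction should be documented before the treatment comparison is run.

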#### 6.4.2.2 Secondary Analysis

Similar analysis also will be performed on secondary PK/PD endpoints between Treatment T and R.

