The PD parameters are used to measure the study drug action over time as measured by the hyperglycemic-euglycaemic clamp procedure. During the clamp procedure, blood glucose concentrations are held constant after the administration of NovoLog[®] by adjusting the exogenous glucose injection rate (GIR). GIR, denoted as G , is defined as infusion rate of glucose administered intravenously needed to maintain target blood glucose level. GIR data will be reported as mg/kg/min.

(1) Primary PD Endpoints

- (i) G_{\max} : Maximum GIR, defined as maximum infusion rate of glucose administered intravenously needed to maintain target blood glucose level.
- (ii) $AUC_{G(0-12h)}$ for GIR: defined as area under the curve (AUC) of GIR, i.e. the total amount of glucose infused over the duration of the clamp procedure.

Both G_{\max} and AUC_G of GIR are calculated based on smoothed GIR curves.

(2) Secondary PD Endpoints

- (i) $AUC_{GA(0-12h)}$ for GA (or G_A), where GA stands for “GIR for IA” to reflect the PD effect of only IA.
- (ii) $G_{A\max}$
- (iii) $AUC_{G(0-last)}$,
- (iv) $AUC_{G(0-2h)}$,
- (v) Value of last measurable GIR, G_{last}
- (vi) Time until maximum glucose infusion rate is reached, $t_{G\max}$
- (vii) Time of start of GIR post-dose, t_{Gonset}

- (viii) Time of last measurable GIR, t_{Glast}
- (ix) $t_{-G50\%early}$, defined as the time to 50% maximal GIR before t_{Gmax}
- (x) $t_{-G50\%late}$, defined as the time to 50% maximal GIR after t_{Gmax}

4) Statistical Analysis

The ratio (T to R) of geometric means and 90% confidence intervals of the ratio of geometric means for primary and secondary endpoints are to be estimated and evaluated.

VII. Safety Evaluation

- (1) Changes in vital signs and ECG from baselines will be analyzed at designated post-dosing time points for two treatments, respectively.
- (2) The results of laboratory tests, including hematology, clinical chemistry and UA, will be assessed. Comparisons between data at Screening and that at the follow-up visit (F/U) will be performed. Unscheduled visit for safety laboratory testing is allowed and at the discretion of PI during the COVID-19 pandemic.
- (3) Adverse events (AEs): The occurrence of AEs will be compared for the two treatments. Two AE of special interests: hypoglycemia and injection site reaction will be closely monitored and elevated.

TABLE OF CONTENTS

1.0	INTRODUCTION.....	19
1.1	Background.....	19
1.2	Rationale for the Proposed Study.....	19

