#### 5.1.2 Secondary Endpoints

- (1)  $t_{max}$  is an observed value, corresponding when  $C_{max}$  appears, and is represented in units of “minutes”, or “min”.
- (2) Partial  $AUC_{IA(t_{m1}-t_{m2})}$ , in units of pg/mL\*hr, can be calculated per the trapezoidal rule and sampling time for each treatment of each subject similarly as the Eq. (14):

$$AUC_{t_{m1}-t_{m2}} = \sum_{i=m_1}^{m_2-1} \frac{C_i + C_{i+1}}{2} (t_{i+1} - t_i) \quad (15)$$

where,  $t_{m1}$  and  $t_{m2}$  are the starting and ending sampling times of PK measurement for the partial  $AUC_{IA(t_{m1}-t_{m2})}$ , respectively;

$m$  is the number of available PK measurements.

The following partial AUC of Insulin Aspart will be calculated: (i)  $AUC_{IA(0-1h)}$ , (ii)  $AUC_{IA(0-2h)}$ , (iii)  $AUC_{IA(0-4h)}$ , and (iv)  $AUC_{IA(4-12h)}$ .

(3)  $AUC_{IA(0-\infty)}$ , in units of pg/mL\*hr, is defined as  $AUC_{0-t^*}$ , with  $t^* > t$  and meets

$$C(t^*) = C_1, \text{ if } C(t) > \max(C_1, QL) \quad (16)$$

where  $C_1$  = baseline, and  $t=12$  hrs, the time point for the last sample collection ;  
 QL is the analytical method's quantitation limit (QL)

When  $C(t) \leq \max(C_1, QL)$ ,

$$AUC_{0-\infty} = AUC_{0-t} \quad (17)$$

Otherwise

$$AUC_{0-\infty} = AUC_{0-t} + AUC_{t-\infty} \quad (18)$$

$AUC_{0-t}$  can be calculated per the trapezoidal rule as given in the Eq. (14).  $AUC_{t-\infty}$  can be obtained per the extrapolation method as given in the Eq. (19) below, based on

$$AUC_{t-\infty} = \int_{t_n}^{\infty} C(t)dt \approx -\frac{1}{K_e} B e^{-k_e t} \Big|_{t_n}^{\infty} = \frac{C_n - C_1}{K_e} \quad (19)$$

where  $C_n = C(t_n)$  is the last available PK measurement for serum IA concentration;  
 $K_e$  is the rate constant of elimination obtained per the method described in the next paragraph; and  
 $B$  is a constant, irrelevant to time.

If the  $AUC_{t-\infty}$  (Eq. (18)) cannot be found as a converged data for a subject, specifically:

- A positive  $K_e$  cannot be found; or
- The obtained  $AUC_{t-\infty}$  is much larger than 30% of  $AUC_{0-t}$ ;

then, the data of  $AUC_{0-\infty}$  for the treatment of the subject can be considered as not available.

(4) The Elimination Rate Constant,  $K_e$ , by Least Square Model

$K_e$  will be obtained by the software output. In case the software cannot report the data of  $K_e$ , then  $K_e$  is calculated based on the least squares model from the logarithm of the last three (3)

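### Every secondary endpoint is given the log-scale ratio analysis, which does not suit the time endpoints and is undefined for partial GIR AUCs that are zero

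*SAP*

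**What the plan says.** SAP 6.4.2.2 disposes of the secondary endpoints in one sentence: "Similar analysis also will be performed on secondary PK/PD endpoints between Treatment T and R". The analysis it points back to is in SAP 6.4.2.1: "PK/PD endpoints will be analyzed using ANOVA methods with the effects of Treatment groups, Period, Sequence and Patient-within-Sequence". The contrast in the CI formula "is the difference of least square means of the logarithms of PK/PD endpoints for treatments T and R", and the interval is then back-transformed to a T/R ratio. Protocol synopsis VI.4 asks for the same thing: "90% confidence intervals of the ratio of geometric means for primary and secondary endpoints are to be estimated and evaluated".

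Neither document exempts any endpoint. Protocol 10.1.3 and 10.1.4 refer only in general terms to descriptive and comparative methods.

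The secondary endpoints in Protocol 2.4 and SAP 2.4 and 5 include:
- times: tmax for insulin aspart (IA) and for human insulin (HI), tGIRmax, tGIRonset, tGIRlast, and the early and late 50% times;
- partial AUCs: for GIR, AUC_GIR(0-2h) in both documents, with 0-1h, 0-4h and 4-12h added by the SAP; and the corresponding IA partial AUCs;
- other magnitudes: AUC_IA(0-∞), AUC_GIR(0-last), GIRlast, CL/F, Vz/F, t1/2, and the GIR measures adjusted to net IA (GA).

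SAP 5.1.2 says that tmax "is an observed value, corresponding when" Cmax appears. The acceptance range, "the 90% confidence interval is within 80.00 – 125.00" per cent, is stated for the primary analyses only. The one rule for zeros is in SAP 5.2.3 and concerns the denominator of the IA fraction.

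**The concern.** A log-scale ratio is the natural summary for a positive concentration or exposure. It is a poor one for a clock time. What a reader wants to know about onset and duration of a rapid-acting insulin is how many minutes earlier or later one product acts. On the log scale the same shift in minutes counts for more when it happens early than when it happens late. Two of the times also have features that sit badly with normal errors on the log scale: PK tmax is tied to an uneven sampling schedule, and tGIRlast is bounded by the end of the clamp.

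The second problem is one of definition. Glucose is infused only after blood glucose has fallen by at least 5 mg/dL (Protocol 7.14.3), so a partial GIR AUC can be zero. The log of zero does not exist, and no rule says what happens then. If the observation is simply lost, so is the subject's T/R comparison for that endpoint. For AUC_GIR(0-1h), the subjects lost would be those whose infusion started latest.

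**Working it through.** **Inputs.** Post-dose sampling times and windows from SAP Table 3; 60 subjects with two clamps each, so 120 clamps; minute-by-minute GIR smoothed over 9 points (SAP 4.4); the infusion rule in Protocol 7.14.3; the model in SAP Eq. (34).

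1. **The plan's own figure.** ln 0.80 = −0.2231 and ln 1.25 = 0.2231, which agree with the stated −0.223 and 0.223. These limits belong to the four primary endpoints.

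2. **One sampling step in PK tmax, as a ratio of adjacent times:**

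| Step (min) | Ratio |
|---|---|
| 5 to 10, 10 to 20 | 2.00 |
| 20 to 25 | 1.25 |
| 30 to 40 | 1.33 |
| 40 to 50 | 1.25 |
| each step from 50 to 80 | 1.10 falling to 1.07 |
| 80 to 90 | 1.125 |
| 120 to 150 | 1.25 |

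   A 10-minute shift from 30 to 40 min is ln(40/30) = 0.288 on the log scale. The same 10 minutes from 80 to 90 is ln(90/80) = 0.118. The first counts 0.288/0.118 = 2.4 times as much.

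3. **What a step does to the reported estimate.** One of 60 subjects moving from 30 to 40 min under T changes the geometric mean ratio by exp(0.2877/60) = 1.005, or about 0.5%. The table describes single-subject ratios, not error in the mean.

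4. **tGIRlast.** GIR is recorded from 0 to 720 min, and SAP 4.3.1 caps the end of GIR at 720. Late values can therefore pile up at the bound.

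5. **Where the log is undefined.**
   - AUC_GIR(0-1h) is zero if infusion starts after 60 min, apart from a few minutes of smoothing overlap. With an assumed step to 4 mg/kg/min at 70 min, the smoothed 0-1h area is 0. With the step at 63 min it is 0.08 mg/kg for a local linear fit and −0.12 mg/kg for a local quadratic one. The SAP does not say which is used, and neither a zero nor a negative value can be logged.
   - AUC_GIR(4-12h) is zero if infusion has ended by 4 h. Protocol 7.14.4 and SAP 4.3.1 both allow GIR to end before the clamp does.
   - tmax for HI is 0 if the highest value is the time-0 sample, provided it is read over the same 26 samples as in Eq. (13).

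6. **What is then lost.** Eq. (34) includes subject within sequence. A subject with only one usable period contributes nothing to the within-subject T−R contrast.

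7. **How often.** The documents do not say. Assuming a chance p of a zero per clamp, independent across clamps, the chance of at least one zero is 1 − (1 − p)^120. That is 11%, 45%, 70% and 91% for p = 0.1%, 0.5%, 1% and 2%.

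8. **Why an improvised rule is risky.** If k zeros under T are replaced by a constant c against a typical value m, a true ratio of 1.00 becomes exp(k·ln(c/m)/60). With assumed c from 0.01 to 1 mg/kg and m from 50 to 300 mg/kg, one zero gives 0.84 to 0.94 and three zeros give 0.60 to 0.82.

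A related slip: Eqs. (27) and (28) as printed end by subtracting t_j. With t_j = 40, half-maximum 4, and adjacent GIR values 3.9 and 4.1, Eq. (27) gives 0.5 − 40 = −39.5 min where interpolation gives 40.5. Taken literally, the 50% times would be negative.

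**The case against.** **No decision depends on this.** That is right. A reader might infer that the biosimilarity conclusion is at risk. The documents do not support that: the hypotheses in SAP 6.4.2.1 name only Cmax, AUC_IA(0-12h), GIRmax and AUC_GIR(0-12h), and no acceptance range is set for secondary endpoints.

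**The sampling-grid argument is narrow.** It is tempting to say that all the time endpoints reflect the sampling schedule, or that they carry a 33% error. Neither follows. GIR is recorded every minute and the 50% times are interpolated, so the grid argument covers PK tmax alone. Even there, the documents do not say whether tmax uses scheduled or actual times. Steps are 7 to 10% in the 50 to 80 min region that SAP 6.1.1 singles out for evaluability, and one subject's 33% step moves the mean ratio by 0.5%. A Hodges-Lehmann difference for tmax still moves in sampling steps; its gain is a result in minutes without a normality assumption. Log-ANOVA on positive times can be computed, and no data in the documents show that its errors are non-normal. The fault for times is one of suitability.

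**A delay would not be hidden.** A reader might infer that losing late starters from AUC_GIR(0-1h) conceals slower onset. A late starter still has a positive tGIRonset and stays in the primary AUC_GIR(0-12h). What is distorted is the early-exposure estimate itself.

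**Zeros may be rare.** This stands. No distribution of onset or end of infusion is given. Protocol 4.2 cites typical clamps of 8 to 10 hours for rapid-acting insulins, which makes an end by 4 h look unusual.

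**The wording is loose.** *Similar* is not *identical*, and the output template is not in the documents. But synopsis VI.4 asks for geometric mean ratios for secondary endpoints, which settles the reading.

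**Conclusion.** The point holds as a matter of suitability and definition for the secondary analyses. As written, the plan applies a log-scale ratio to times, where a difference in minutes is the interpretable quantity, and to partial GIR AUCs whose log may not exist, with no rule for that case. The loss per affected subject is complete for that endpoint, and for AUC_GIR(0-1h) it is selective towards late starters. The total effect cannot be sized from the documents: the probabilities and replacement effects in the working rest on assumed zero rates, constants and typical values, and the real frequency may be low. The consequence is confined to supportive estimates of onset, duration and early or late effect. It is still worth settling before unblinding, because a zero rule chosen afterwards could move the estimate by several per cent or more.

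**What to change.** Replace the sentence in SAP 6.4.2.2 with a short paragraph, and match the wording in Protocol synopsis VI.4:

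- **Exposure and magnitude endpoints, when all values are positive:** keep the log-ANOVA ratio with 90% CI. This covers AUC_IA(0-∞), partial AUC_IA, AUC_GIR(0-last), partial AUC_GIR, the GA endpoints, GIRlast (a rate, not a time), CL/F, Vz/F and t1/2.
- **Time endpoints (tmax for IA and HI, and all tGIR endpoints):** report the Hodges-Lehmann T−R difference in minutes with a 90% CI. Form each subject's period 1 minus period 2 difference and compare the two sequences. The shift between sequences TR and RT estimates twice the treatment difference, so halve it and its limits.
- **Any partial AUC with one or more zeros (or negative values after smoothing):** analyse the T−R difference on the original scale in the same crossover model, with those values kept, and report the number of zeros by treatment.

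Separately, correct the sign of t_j in Eqs. (27) and (28).

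The cost is one SAP paragraph, a line in the synopsis and standard code. No data collection changes. The time endpoints, and any partial AUC with zeros, lose a ratio-scale CI.
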